13.9 Temperature and Humidity

Mean, median, standard deviation, minimum and maximum room temperature, and humidity will be computed.

13.10 Data Evaluability

Blood glucose data will be considered not evaluable for the following reasons:

- Samples with no associated or valid hematocrit value.
- Samples with no associated or valid Cobas 6000 value.

• Failure to begin to separate the plasma from the red cells within 10 minutes of obtaining the first meter test.

- The collected samples exceed a maximum of 5 h of sample withdrawal time, and will be kept at room temperature $(23 \pm 5 \, ^{\circ}\text{C})$ before evaluation.
- For a given sample, the meter is missing a replicate.
- Results of the glucose analyzer blood sample are not within ±4% of each other, 100* (Rep2-Rep1)/Rep1, or ±4mg/dL (0.22mmol/L) of each other (Rep2-Rep1) if the average falls below 100mg/dL (5.5mmol/L).

14.0 Data Management

- **14.1** A unique number will identify each subject/sample. The unique number will be entered on the CRFs. The site will create a procedure to de-identify subjects from samples so that the staff members documenting subject names will not have access to sample results and the staff members testing the samples will not have access to subject names. A master list of subject names, with their subject IDs, will be kept by the Investigator at the study site until the study has been closed.
- **14.2** Study personnel will complete and sign all appropriate forms in compliance with GCP. CRFs should be completed legibly, in black or blue ink. If it is necessary to make corrections, a single line should be drawn through the original entry, the new entry is written in, and the correction initialed and dated by the individual correcting the CRF.
- **14.3** Study data will be primarily collected through an electronic data capture (EDC) system used by Ascensia. The data will be recorded on forms by designated study staff that will serve as source documents and entered into the EDC system. All source forms will be retained by the site.
- **14.4** In addition to data collection, the EDC system will be used for data cleaning as well as monitoring operations. Site users will be trained on this system before the start of the study and their access to EDC system will be contingent upon successful completion of training requirements.

15.0 Amendments to the Protocol

- **15.1** Any change to this protocol requires a protocol amendment (or revision) unless the IRB agrees to an administrative change (for minor changes).
- **15.2** Determine the justification(s) for the protocol revision, impact of the changes on subject safety, the clinical or statistical significance of the data, impact of changes on the clinical investigators and their staff, and impact on timely completion of the clinical trial.
- **15.3** Determine if the revision meets the criteria of a Substantial Amendment.

15.4 Substantial Amendments

15.4.1 Substantial amendments to the conduct of the clinical trial may arise from changes to the protocol or from new information relating to the scientific documents in support of the trial. Substantial changes require notification to the overseeing IRB before implementation. For any questions on whether a change would be considered substantial, consult with the respective IRB.

- 15.4.2 Amendments to the trial are regarded as "substantial" where they are likely to have a significant impact on the:
 - Safety, health or rights or physical or mental integrity of the subjects,
 - Scientific value of the trial including robustness or reliability of the data generated by the study,
 - Conduct or management of the trial,
 - Quality or safety of any investigational product used in the trial.
- 15.4.3 An amendment is only to be regarded as "substantial" when one or more of the above criteria are met but the IRB may have additional requirements that shall be considered.
- 15.4.4 Examples of substantial amendments may include (but are not limited to):
 - New tests
 - Increase in the number of visits due to safety issues associated with the ongoing trial
 - Change of inclusion/exclusion criteria
 - Change in the number of participants
 - Updated PI
 - Informed Consent Form (ICF)
 - Updated investigator brochure with relevant safety information
 - Change in the management of the study
 - Temporary halt to the study or restart of the trial after a temporary halt
- **15.5** Once justified, the protocol changes can be drafted and the changes documented in the Revision History. The changes are to be incorporated directly into the body of the protocol document itself (revised protocol).
- **15.6** Once the drafted revision is approved internally and by the PI, it will be submitted to the IRB, where required. All subsequent, IRB-approved, revised protocols would be numbered sequentially.

Protocol /CIP: GCA-PRO-2021-003-01 - Amendment 1 Ascensia Diabetes Care

Version: 14Oct2022 CONFIDENTIAL

15.7 The amended protocol will be approved by the original approvers, including the sponsor representatives or designee and the PI.

15.8 The sponsor must assure that each investigator (and his/her staff) is following the most recent IRB approved amendment or revised protocol as the study proceeds. The sponsor must ensure that the study monitors, investigator(s) and study staff have been trained with respect to any recent protocol amendments and revisions prior to implementation.

16.0 Deviations from the clinical protocol

- **16.1** A protocol deviation is any alteration or modification to the procedures described in the protocol. The investigator is not allowed to deviate from the protocol. The only exceptions to this are:
 - 16.1.1 The deviation is necessary to protect the subject's rights, safety and well-being, or the scientific integrity of the clinical investigation without prior approval of the sponsor and IRB.
 - 16.1.2 Prospective deviations that broaden the scope of the protocol (waivers of the protocol) are prohibited. Under emergency circumstances, these instances can proceed.
- **16.2** Procedures for recording, reporting and analyzing protocol deviations will include recording the deviation on a Protocol Deviation log form to be supplied by the Sponsor.

17.0 Device Accountability

- **17.1** Description of the procedures for the accountability of investigational devices as follows:
 - 17.1.1 Access to investigational devices shall be controlled and the investigational devices shall be used only in the clinical investigation and according to the protocol.
 - 17.1.2 The sponsor shall keep records to document the physical location of all investigational devices from shipment of investigational devices to the investigation sites until return or disposal.
 - 17.1.3 Accountability: The PI or a delegate shall keep records documenting the receipt, use, return and disposal of the investigational devices, (including unused, expired or malfunctioning devices), which shall include:
 - Date of receipt
 - Identification of each device (serial number of meter or strip lot)
 - The expiry date, if applicable
 - Date(s) of use
 - Subject number

• Date of return of unused, expired or malfunctioning investigational devices, if applicable

18.0 Regulatory

Ascensia (sponsor) has determined that according to IDE requirements of 21 CFR 812.2(c), this IVD study meets all conditions for IDE exemption and therefore submission of an IDE application to FDA is not required. Determination is based on the following:

The Contour Next and Contour Plus Elite Glucose Monitoring Systems (IVDs);

- are labeled in accordance with 21 CFR 809.10(c)
- are non-invasive
- do not require an invasive sampling procedure that presents significant risk
- do not by design or intention introduce energy into a subject
- are not used as a diagnostic procedure without confirmation of the diagnosis by another, medically established diagnostic product or procedure.

18.1 IRB Approval

- 18.1.1 Before study initiation, an IRB must review this protocol, the ICF, and any other supporting study documents which impact subject safety. The IRB will determine if the Informed Consent is required according to local regulations and requirements or if consent is not required (ISO 20916:2019(E)).
- 18.1.2 The investigational site may not begin the study until the IRB has given its written and dated approval via a letter that identifies the version/date of the protocol and ICF, if applicable, or a notification that consent is not required.
- 18.1.3 A copy of the IRB approval letter must be provided to the Investigator and to sponsor prior to the SIV.

18.2 Study Documentation Procedures

- 18.2.1 The investigator will keep study records for a minimum of three years. Alternatively, other arrangements may be made with Ascensia for study document storage.
- 18.2.2 Study Investigational Devices will be labeled "For Investigational Use only. The performance characteristics of this product have not been established" for this study.
- 18.2.3 After study completion, all BGMSs will be disinfected before they are returned to Ascensia. A decontamination log will be completed for the used meters. The meters, unused strip vials, control solutions, and meter UGs will be accounted for at the site and returned to the Ascensia Study Manager upon completion of the trial.

Protocol /CIP: GCA-PRO-2021-003-01 - Amendment 1 Ascensia Diabetes Care CONFIDENTIAL

18.3 Investigator's Report of Study Closure

Version: 140ct2022

18.3.1 Sponsor representatives will notify the site that the study is closed. The study will be considered closed when the data has been locked for data analysis.

- 18.3.2 The Investigator or designee will submit a report summarizing subject disposition and other study details, as appropriate, to the Study Manager and the IRB. This report will be completed within 3 months of the study closure date.
- 18.3.3 In addition, the Study Manager, or designee, will report the completion of the study to the IRB within 6 months of study closure.

19.0 Statements of compliance

- **19.1** This clinical investigation will be conducted in compliance with applicable requirements:
 - 19.1.1 Protection of Human Subjects regulations in 21 CFR part 50.
 - 19.1.2 IRB regulations in 21 CFR part 56.
 - 19.1.3 Investigational Device Exemptions regulations in 21 CFR part 812.
 - 19.1.4 Declaration of Helsinki.
 - 19.1.5 CLSI. Point-of-Care Blood Glucose Testing in Acute and Chronic Care Facilities; Approved Guideline - Third Edition. CLSI document POCT12-A3. Wayne, PA: Clinical and Laboratory Standards Institute; 2013.
 - 19.1.6 International Standards: ISO20916:2019(E) In vitro diagnostic medical devices Clinical performance studies using specimens from human subjects – Good Study Practice and In Vitro Diagnostic Regulation 2017/746 Annex XIII, Part 2.
 - 19.1.7 British Standard BS EN 13612:2002, "Performance evaluation of in vitro diagnostic medical devices."
- **19.2** The clinical study shall not begin until the required approval from the IRB or regulatory authority have been obtained.
- **19.3** Clinical trial insurance shall be provided as appropriate.

20.0 Informed Consent Process

The IRB will determine if the Informed Consent is required according to local regulations and requirements for use of residual blood samples for this study.

The following will only apply if Informed Consent is required by the IRB. If the IRB determines that consent is not required, this section will not apply.

Protocol /CIP: GCA-PRO-2021-003-01 - Amendment 1 Ascensia Diabetes Care CONFIDENTIAL

20.1 Since the subject is a neonate, the subject's parent/guardian - Legally Authorized Representative (LAR) - will complete the informed consent process before performing any study procedures.

- 20.2 The LAR will be informed about the study objectives, investigational devices, study procedures, expected study duration, and risks of study participation.
- 20.3 Study participation is voluntary. The information will be given in written form (ICF) as well as verbally by the investigator.
- **20.4** The subject's LAR will sign and date the ICF. The ICF will then be dated and signed by the investigator.
- **20.5** The investigator will retain the original of the documents. The subject's LAR will receive a copy of the ICF and if applicable, insurance terms and conditions.

21.0 Adverse events and adverse device effects

Version: 140ct2022

The procedures to be performed under this protocol are considered to be of low risk since the glucose testing procedures will use residual samples which are remnants of neonatal blood collected as part of routine prescribed practice.

Due to the nature of this study, no adverse events (AE) are expected as per the following:

- 21.1 This study only includes residual ('left-over') samples of blood collected by standard, approved technique for prescribed tests.
- 21.2 No neonate will be exposed to any of the BGMS at any point; all study activities will be conducted in the institution's lab.
- **21.3** The samples will be de-identified in order to protect the confidentiality of the subjects. Confidentiality issues are mitigated due to the fact that the nursing staff overseeing the babies will not be informed of any study results, and samples will be de-identified prior to being given to the laboratory staff who perform study testing
- **21.4** Regardless of the above, any experience that the investigator considers to be an AE will be documented and reported immediately to Ascensia.

21.5 Definition of Adverse Events

21.5.1 Adverse Event (AE): Adverse event refers to any untoward medical occurrence, inappropriate patient management decision, unintended disease or injury, or untoward clinical signs in subjects, users, or other persons, with any connection to to study related activities, whether or not related to the IVD medical device under investigation.

Protocol /CIP: GCA-PRO-2021-003-01 - Amendment 1 Ascensia Diabetes Care

Version: 14Oct2022 CONFIDENTIAL

21.5.2 Adverse Device Effect (ADE or Adverse Effect): Any AE resulting from insufficient or inadequate instructions for use, installation, operation, or any malfunction of the IVD medical Device under investigation. This includes any AE resulting from use error or from unintentional misuse of the device.

- 21.5.3 Serious Adverse Event (SAE): Refers to an AE that led to any of the following:
 - a) death,
 - b) serious deterioration in the health of the subject, users or other persons as defined by one or more of the following:
 - 1) a life-threatening illness or injury, or
 - 2) a permanent impairment of a body structure or a body function including chronic diseases, or
 - 3) in-patient or prolonged hospitalisation, or
 - 4) medical or surgical intervention to prevent life-threatening illness or injury or permanent impairment to a body structure or a body function,
 - c) fetal distress, fetal death, or a congenital abnormality or birth defect, including physical or mental impairment.
- 21.5.4 Serious Adverse Device Effect (SADE): Adverse device effect that has resulted in any of the consequences of an SAE.

21.6 Adverse Event Classification

Table 3. Classification of Adverse Events (ISO 20916: 2019)

Adverse Events	Non -device related	Device related		
	Applies to : Interventional Studies Sampling procedure causes direct harm to the subject	 Applies to: Interventional Studies: inaccurate test result leads to indirect harm to the subject. Sampling procedure causes direct harm to the subject 		
Non-Serious	Adverse event (includes all categories)	Adverse device effect		
Serious	Serious Adverse event (includes all categories that are serious)	Serious adverse device effect		
		Anticipated	Unanticipated	
		Anticipated Serious adverse device effect	Unanticipated Serious adverse device effect	

21.7 Adverse Event Reporting

- 21.7.1 AEs will be documented during this study by completing the AE Form. The Investigator or designee will sign and date an AE Form for each AE that is observed.
- 21.7.2 AEs will be evaluated by a member of the study staff and the PI. The nature of each event and date of onset, outcome, course, maximum intensity and action taken for treatment should be established. Details of any corrective treatment should be recorded on the AE Form.
- 21.7.3 Investigators should follow up on the status of any AE until the event has been resolved, or until the condition has stabilized.
- 21.7.4 The Investigator or designee will notify the Study Manager or Study Monitor within 24 hours of any SAE that occurred during the study. Ascensia will promptly review all information relevant to the safety of the investigational device.
- 21.7.5 Upon the receipt of a report of an SAE by the Ascensia Study Manager or Monitor, the report will be immediately forwarded to:

22.0 Handling and Reporting of Device Deficiencies

- **22.1** Any functional problems with the investigational BGMS will be considered a device deficiency and will be documented by the study staff and reported timely to Ascensia.
- **22.2** The study staff should be specific about describing the problem and the sequence of events that led to it. All information will be documented on the Data Deficiency Form, including the meter type, serial number, and test strip lot.
- **22.3** Malfunctioning BGMs will be replaced and this will be documented for device tracking.
- **22.4** All device deficiencies related to the identity, quality, durability, reliability, safety or performance of an investigational medical device shall be documented throughout the clinical investigation and appropriately managed by the sponsor.
- **22.5** Device deficiencies that did not lead to an AE but could have led to a medical occurrence shall be reported to the sponsor without delay.
- **22.6** All device deficiencies are to be reviewed and documented in writing whether they could have led to a SADE.

23.0 Vulnerable population

23.1 While the samples will be taken from neonates, who are in the vulnerable population category, the procedure does not involve additional risk since the samples are residual with no additional sampling required.

23.2 If the IRB determines consent is required, then proxy consent by an LAR shall be provided to protect the rights of the subject.

24.0 Suspension/Premature termination and Subject Withdrawal Criteria

- **24.1** In the event the study is prematurely suspended or terminated, the sponsor shall be notified as well as the IRB.
- **24.2** The subject's sample may be withdrawn from the study at the discretion of the Investigator.

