3.0 Synopsis of the Clinical Study

Design Type:	Open Label, prospective, single arm study		
Investigational Devices:	CONTOUR NEXT ® Blood Glucose Monitoring System (BGMS)		
	CONTOUR PLUS ELITE® Blood Glucose Monitoring System		
Trial objective	The purpose of this study is to extend the intended use of two BGMSs to include testing of neonatal blood by Health Care Professionals in a clinical setting for the quantitative measurement of glucose levels in neonates.		
	This trial will evaluate the performance of both the CONTOUR NEXT BGMS and CONTOUR PLUS ELITE BGMS using blood from neonates within a hospital ward, e.g. routine/newborn nurseries, Special Care Nurseries, Neonatal Intensive Care Unit (NICU). The investigational BGMSs will be tested by a Point-of-Care operator using residual heel-stick capillary blood samples from neonates who underwent routine prescribed testing.		
Reference Analyzer	Cobas® 6000		
Sample size:	A total of 120 blood samples tested in duplicate with N=240 evaluable results are required for this study. Therefore, at least 120 subjects will be enrolled. Up to 200 subjects may be enrolled to obtain the required number of samples.		
	A sub-group of at least 5 capillary whole blood samples will be tested in neonates who are less than 24 hours of age. A sub-group of at least 5 capillary whole blood samples will be tested in neonates from the NICU.		
Inclusion and Inc	clusion Criteria		
Exclusion •	Residual capillary (heel-stick) blood samples collected from neonates (less		
criteria:	than 28 days of age) after birth as part of prescribed testing.		
•	Sample blood volume must be sufficient to complete investigational testing		
	in addition to routine prescribed clinical laboratory testing.		
Ex	clusion Criteria		
•	Samples from subjects who are ≥ 28 days of age.		
•	Samples from subjects who have previously been enrolled into this study.		

Ascensia Diabetes Care
CONFIDENTIAL

Protocol /CIP: GCA-PRO-2021-003-01 - Amendment 1 Version: 14Oct2022

Objectives The primary objective of the study is to evaluate the performance of NEXT and CONTOUR PLUS ELITE BGMSs with residual neo samples. The performance of the BGMSs will be analyzed according objectives:					
Primary Objective:					
• At least 95% of all blood glucose results shall fall within ±12.5% of reference values (laboratory method) for glucose concentration ≥100 mg/dL mmol/L) and within ±12 mg/dL (±0.67 mmol/L) at glucose concentration <100 mg/dL (5.55 mmol/L).					

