8.0 Clinical Study Design

- 8.1 This is an open label, prospective, single arm study. The results of the study devices will be compared to the laboratory analyzer results from the same blood sample.
- For each BGMS, 120 evaluable samples (N=240 evaluable results due to duplicate testing) 8.2 are required. Therefore at least 120 subjects will be enrolled. Up to 200 subjects may be enrolled to obtain the required number of samples.

Protocol /CIP: GCA-PRO-2021-003-01 - Amendment 1 Ascensia Diabetes Care

Version: 14Oct2022 CONFIDENTIAL

8.3 Randomization:

- 8.3.1 Since two BGMSs will be tested in the study, the order of testing the study devices will be randomized.
- 8.3.2 Three strip lots (per BGMS) will be tested, with each sample tested with one lot. The strip lots will be randomized.
- **8.4** The results from these two BGMSs will not be compared to each other.
- **8.5** The study design follows CLSI- POCT12-A3:2013 and ISO 20916:2019(E) to ensure it is scientifically robust and valid.
- 8.6 Subjects with non-evaluable data will be replaced as needed to obtain N=120 samples, and N= 240 results (duplicate results) for each BGMS.

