10.1 Recruitment and Enrollment

- 10.1.1 A total of at least 120 blood samples with evaluable results (N=240) are required for this study. Up to 200 subjects may be enrolled into the study to obtain the required number of samples. See section 13.10 for the definition of evaluability.
- 10.1.2 The subject population will consist of neonates from hospital wards (e.g. routine/newborn nurseries, SCN, NICU) of the clinical investigational site.
- 10.1.3 There will be a sub-group of at least 5 samples collected from neonates who are less than 24 hours of age.
- 10.1.4 There will be a sub-group of at least 5 samples collected from neonates from the NICU.
- 10.1.5 The samples in these two sub-groups are permitted to overlap.
- 10.1.6 The study staff will document subject demographics, including age and gender.

Ascensia Diabetes Care

CONFIDENTIAL

Protocol /CIP: GCA-PRO-2021-003-01 - Amendment 1 Version: 14Oct2022

10.1.7 Unused residual blood samples collected for study testing procedures will be discarded according to hospital Laboratory Safety Guidance (Occupational Safety and Health Administration) procedures.

10.2 Inclusion Criteria

- 10.2.1 Residual capillary (heel-stick) blood samples from neonates (less than 28 days of age) after birth as part of prescribed testing.
- 10.2.2 Sample blood volume must be sufficient to complete investigational testing in addition to routine prescribed clinical laboratory testing.

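### Section 24.2 lets the Investigator withdraw samples with no stated reason, timing or analysis handling, so withdrawal after results are known is permitted and could raise both primary percentages

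*Combined protocol and SAP*

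**What the plan says.** Section 24.0 is titled as giving subject withdrawal criteria. Its only sentence on samples, 24.2, reads: "The subject's sample may be withdrawn from the study at the discretion of the Investigator".

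The provisions that bear on it are these.

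- **Exclusions.** Section 13.10 opens "Blood glucose data will be considered not evaluable for the following reasons" and gives six objective reasons: no valid hematocrit, no valid Cobas value, late plasma separation, sample too old, missing meter replicate, and discordant Cobas duplicates. Withdrawal by the Investigator is not among them.
- **Replacement.** Section 8.6: "Subjects with non-evaluable data will be replaced as needed to obtain N=120 samples". Section 10.1.1: "Up to 200 subjects may be enrolled into the study to obtain the required number of samples".
- **Final number.** Section 13.5.3 says that if the count is not exactly 240, the critical values become about 95% and 98% of the results available.
- **Masking.** The synopsis describes an "Open Label, prospective, single arm study". Two separations are stated. In Section 14.1, staff who document names do not see sample results, and "the staff members testing the samples will not have access to subject names". In Section 21.3, "the nursing staff overseeing the babies will not be informed of any study results". Neither names the Investigator, who keeps the master list of subjects (14.1).

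**The concern.** Each criterion is a count of accurate results against a fixed cut: 228 of 240 for criterion 1 and 236 of 240 for criterion 2. Once a sample has been tested, its only role in those counts is to add accurate or inaccurate results. A rule that allows its removal at that point, with no reason or time limit, leaves the content of the denominator open to a decision made with the results in view.

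The usual safety argument for open discretion is weak here. Residual blood is tested in a laboratory, no subject is exposed to a device, and no treatment follows from the results (Sections 9.2, 21.2 and 25.0). At stake is the false-pass chance of about 5% that Section 13 gives for each criterion.

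**Working it through.** **Inputs from the plan.** n = 240 results from 120 samples in duplicate. Cuts are 228 and 236 (13.5.2, 13.5.3). Unacceptable true accuracy is 92.03% for criterion 1 and 96.23% for criterion 2. The enrolment ceiling is 200, so 200 − 120 = 80 samples are available beyond the minimum.

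**Inputs that are assumptions.** The number of samples withdrawn (k), the choice of the most inaccurate ones, and the agreement within duplicate pairs. The documents give none of these.

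**Step 1: the plan's own figures.** With independent results, P(X ≥ r) = Σ C(240, x) pˣ (1 − p)²⁴⁰⁻ˣ for x from r to 240.

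- Criterion 1: P(X ≥ 228 | p = 0.9677) = 0.9503 and P(X ≥ 228 | p = 0.9203) = 0.0503.
- Criterion 2: P(X ≥ 236 | p = 0.9623) = 0.0502.

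The planned false-pass chance of about 5% is reproduced for both criteria.

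**Step 2: the margin.** Misses allowed are 240 − 228 = 12 and 240 − 236 = 4. Expected misses at the unacceptable accuracy are 240 × 0.0797 = 19.1 and 240 × 0.0377 = 9.0.

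**Step 3: removal without replacement, at the boundary.** Dropping one sample leaves 238 results. The rescaled cuts are 0.95 × 238 = 226.1, so 227, and 0.98 × 238 = 233.2, so 234.

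- Criterion 1: 227/240 = 94.6% fails. Dropping one sample with both results inaccurate gives 227/238 = 95.4%, a pass. Dropping one with a single inaccurate result gives 226/238 = 94.96%, still a fail.
- Criterion 2: 235/240 = 97.9% fails. Dropping one sample with a single inaccurate result gives 234/238 = 98.3%, a pass.

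**Step 4: removal with replacement.** Simulation of 120 pairs at the unacceptable accuracy, 60,000 runs per case. The k samples with the most inaccurate results are removed and replaced by fresh random samples from the same system. Each criterion is taken alone, for one meter system. Duplicates are independent, as the plan assumes.

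| Samples removed | Criterion 1 passes | Criterion 2 passes |
|---|---|---|
| 0 | 5.0% | 5.1% |
| 2 | 14.2% | 19.2% |
| 4 | 27.3% | 42.6% |

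**Step 5: sensitivity.**

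- Without replacement and with the rescaled cuts (20,000 runs), two removals give about 10.5% and 21%, and five give about 33% and 61%. The inflation does not depend on replacement.
- If the second result copies the first with probability 0.5, the pass chances for 0, 2 and 4 removals with replacement are about 9%, 30% and 56% for criterion 1, and 9%, 41% and 72% for criterion 2. The rise from 5% to 9% at zero removals comes from dependence between duplicates and has nothing to do with 24.2.
- If samples are removed without regard to their results, the expected percentages do not change.

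**The case against.** The strongest reply has four parts.

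1. **The text does not say that withdrawal may happen at any time and for any reason.** That is correct: it is read from discretion with no stated limit. But 24.2 is an express permission, and nothing elsewhere narrows it.

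2. **Replacement is not established.** Section 8.6 replaces subjects with non-evaluable data, 10.1.1 refers to 13.10 for that term, and 13.10 does not list Investigator withdrawal. Read literally, a withdrawn sample with complete data triggers no replacement. This stands as an ambiguity. It does not remove the problem, because 13.5.3 rescales the cut to the results that remain.

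3. **Laboratory staff run the tests, and roles are separated.** This makes result-driven withdrawal less likely. No section says that the meter-reference difference is computed or reviewed at the site. But none keeps the Investigator from the meter and Cobas values recorded there.

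4. **The percentages are a worst case.** They require someone to pick out exactly the least accurate samples. This stands, and the figures should be read as an upper illustration for each number removed.

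Two stronger readings are tempting, and the documents do not support them. A reader might infer that selective removal would leave no trace. In fact Section 18.3.2 requires a subject disposition report, sample IDs are sequential (11.4.5), source forms are retained (14.3) and monitoring visits are planned (12.2). What is missing is any duty to record the reason, its timing relative to results, or the effect on the percentages. A reader might also infer a conflict with Section 20.3, "Study participation is voluntary". Section 20 applies only if the IRB requires consent, and a permission given to the Investigator does not deny a parent or guardian the right to withdraw.

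**Conclusion.** The point holds as a gap in protection against bias. Section 24.2 permits removal of a tested sample outside the objective list in 13.10, in an open-label study where no section masks the Investigator to results. Both primary percentages could rise as a result, with or without replacement.

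The margins are thin enough for a few samples to matter. In the worst case in the table, two result-driven removals roughly triple the false-pass chance for criterion 1 and nearly quadruple it for criterion 2. These sizes rest on targeted removal, on the assumed number removed and on independent duplicates. The documents do not show that such removal is intended or expected. The change is worth making because it is cheap and the pass/fail claim would otherwise be open to an avoidable challenge.

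**What to change.** Amend Section 24.2 as follows.

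- **Before results.** The Investigator may withdraw a sample for a documented reason recorded before any meter or Cobas result for that sample is known.
- **After that point.** A sample may be excluded only for a reason in 13.10, for failure of the eligibility criteria in 10.2 or 10.3, for a documented sample identification error, or for withdrawal of consent or an IRB requirement where applicable.
- **Replacement.** State in 8.6 whether withdrawn samples are replaced.
- **Reporting.** List every withdrawn sample with date, time, reason and any results obtained. Repeat both primary percentages including any sample withdrawn after testing whose data may still be used.

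The cost is a short amendment, one listing and one repeat of an existing calculation. No extra blood or testing is needed. The downside is small: the Investigator loses open-ended discretion once a sample has been tested, while objective grounds for removing an ineligible or misidentified sample remain.
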